- 1) **Personalized Genomic Testing for Skin Cancer – Maximizing Utility and Reach – 05/16/17**
- (v. 10)
- 2) **IRB Review History N/A**
- 3) **Objectives**

This study will have two phases, with an added usability test after Phase I and before Phase 2. Phase 1: Cognitive Interviews in Spanish.

Phase 2: Personalized Genomic Testing for Skin Cancer (PGT-SC).

The overarching goal of this study is to learn more about how to maximize the availability, comprehension and appropriate uptake of personalized genomics among different populations in New Mexico. The proposed study has been funded as an R01 by NCI for three years.

Aim I: To examine the personal utility (that is, how does personal genomic testing help the individual) of Personal Genomic Testing for Skin Cancer (PGT-SC) in terms of short-term (three months after testing) sun protection, skin screening (i.e., behaviors), communication, melanoma threat and control beliefs (i.e., putative mediators of behavior change). Guided by Protection Motivation Theory (Robberson and Rogers, 1998), **we hypothesize that behaviors and putative mediators will be higher in those who test, compared to those who decline testing or wait-list controls.**

Aim Ia. An important challenge of personal genomics involves the potential for those who receive “negative” genetic feedback to increase risky behaviors (McBride et al., 2010). To examine this potential unintended consequence of testing, we will conduct a subgroup analysis among those who receive average risk PGT-SC findings, examining sun protection at three months as the outcome. Predictors will include baseline skin cancer threat and control beliefs, skin cancer risk factors, and demographics. These findings will be used in future studies to develop messages for groups that receive average risk feedback, which accounts for large segments of those tested for moderate risk susceptibility factors across many diseases.

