University of New Mexico (UNM) primary care patients are receptive to skin cancer genomic communication; UNM Hispanics report higher skin cancer misconceptions. Drs. [name] and [name] conducted a pilot study in the UNM 1209 Clinic to examine 1) patients' receptivity to behavioral research studies in skin cancer and genetics, 2) to document levels of sunscreen and protective clothing use, shade-seeking, and health provider skin cancer screening examinations, 3) to examine prior health information-seeking and family cancer discussions, and 4) prevalence of accurate skin cancer beliefs. Most (71%) participants were female and they ranged in age from 19-81 years (n=50), with racial/ethnic subgroups consistent with the Albuquerque population (46% were Hispanic, 35% were Non-Hispanic White, 6% Native American, 3% African American, and 10% other). Nine percent had not completed high school, and 55% had household incomes less than \$30k/year. About one third (30%) reported a family skin cancer history and 7% a personal skin cancer history. About two-thirds (66%) reported interest in behavioral skin cancer research, and while few (17%) had heard of genetic testing marketed directly to consumers, two thirds (76%) said they would be interested in learning more about genetic testing for skin cancer. Sun protection and skin cancer screening levels were consistent with recent national data; 29% reported that they consistently used sunscreen, 62% wore a shirt with sleeves, 34% a hat, and 47% sought shade often or always while outside on a sunny day. Even fewer (26%) had ever received a health provider skin examination. Non-Hispanic Whites reported more consistent use of sunscreen, and were more likely to have received a prior health provider skin examination than Hispanics and other racial/ethnic groups (all p values <0.01). Two-thirds (62%) reported that they were moderately or highly likely to develop skin cancer. Predominant reasons for heightened risk included current or past sun exposure, fair skin, and family history or genetic factors. Spontaneous health information-seeking was common, with 72% reporting that they had ever sought information on medical topics, predominantly via the internet. Over half (62%) had sought cancer information. About half (55%) had talked about cancer risk, and 37% about skin cancer risk, in their family. Those with higher perceived skin cancer risk talked more about it with their family ($r=0.34$, $p=0.001$) and were more interested in skin cancer behavioral research participation ($r=0.26$, $p=0.01$). We assess skin cancer misconceptions as an explanation for reduced PGT-SC reach in Aim II of the current study, because Hispanics reported more skin cancer misconceptions than Non-Hispanic Whites in our UNM pilot study. Over half of Hispanics endorsed confusion about which skin cancer recommendations to follow, and significant proportions of Hispanics agreed with the statement "it seems likely almost everything causes skin cancer" (24%); and "people with skin cancer would have pain or other symptoms prior to diagnosis" (24%; Torres et al., 2014). Also in our prior work with nationally representative samples, we found that Non-Hispanic Whites had higher awareness of accurate skin cancer causes, prevention strategies, and symptoms than Hispanics. Hispanics reported higher levels of information overload and misconceptions. ([name] et al., 2009).

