In Phase II, patients will be eligible for the study if they have been registered at a UNM Clinic for six months and assigned a primary care provider, aged >18, and are fluent in either English or Spanish. We will exclude adults that are unable to consent, individuals who are not yet adults (infants, children, teenagers) and prisoners. Pregnant women will be eligible to participate. All participants in Phase II will be consented and interviewed at 1209 University Clinic, OSIS Orthopedic Clinic at [name], the Family Medicine Clinic, the Center for Employee and Occupational Health Services, both at [name] or the North Valley Clinic. Individuals who usually attend another UNM Clinic (Atrisco Heritage Center for Family and Community Health, Northeast Heights Clinic, North Valley Clinic, Westside Clinic, Southeast Heights Center for Family and Community Health, Family Medical Center, Lobo Care Clinic, Senior Health Center, or Southwest Mesa Center for Family and Community Health) and are accompanying a patient from these Clinics will be eligible for Phase II.

6) Number of Subjects (Recruitment Target)

Phase 1: We anticipate that we will conduct cognitive interviews of **40** subjects fluent in Spanish, 20 men and 20 women, who either completed high school or did not complete high school (see phase I recruitment table).

Phase I Recruitment Table

Gender

Education	Male	Female
Completed high school/equivalent or greater	10	10
Did not complete high school or equivalent	10	10

Usability Phase: We will conduct the usability survey in **up to 10** subjects who attend the 1209 Clinic.

Phase II: We anticipate that we will conduct a baseline assessment of **650** subjects (see SOMBRA Study Flow, p. 6). They will then be randomized to a “Wait List Control Group of **120** subjects and a PGT-SC group of **530** subjects. All **530** subjects will be offered MC1R genetic testing. The “Wait List Control Group (**120** subjects) will be offered the MC1R test after the **Three Month Follow Up Questionnaire**. Accordingly, all **650** subjects will be offered MC1R testing. Of those offered, based on our prior experience, we anticipate 30-50 percent will accept an invitation for testing.

Phase II: Recruitment Tables	Ethnicity	
	Hispanic	NHW
Waitlist Controls – n = 120	60	60
PGT-SC Group – n=530	265	265

7) Recruitment Methods

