C) Baseline Assessment. All participants approached will be asked to complete a three minute Eligibility Screening and a Screening Survey to determine their interest in and eligibility for study participation, as well as basic demographics. If they are eligible and interested in study participation, the PA will fully explain the study and the participant will provide written informed consent (Consent - Number 2 and UNMHSC_HIPAA_Authorization), receiving a copy of the signed consent form. The PA will guide them to complete the Baseline Questionnaire in the clinic in a semi-private space with dedicated study computer (tablet or laptop computer).

Based on prior research, we anticipate that 30% of those approached will participate and complete the Baseline Questionnaire. Sample size estimates indicate that a total number of participants of 885 is necessary to evaluate our outcomes.

After completion of the Baseline Questionnaire facilitated by the PA, participants will receive a \$15 Target Gift card for their time and effort. They will sign a Sombra Gift Card Form and receive a Sombra Appointment Card. They will then be randomized to Group 1 - wait-list controls or to Group 2 to consider PGT-SC through a secure website (randomized and balanced across Hispanic and Non-Hispanic ethnicity, n=120 in control arm, n=530 in PGT-SC arm). "Hispanic" ethnicity will be recorded by self-report. Patients will choose Spanish or English study materials.

D) PGT-SC Invitation. (Group 2 – n=530)

Participants randomized to the PGT-SC study arm will view materials on the SOMBRA Website via Internet from a home, work, library or community-based organization computer, or alternatively through a paper version of the modules if they prefer. Internet reach in Albuquerque is >80% and WiFi is available throughout the city. All participants will be asked to consider the four educational modules regarding PGT-SC. The PGT-SC modules are:

- 1) What genetic testing can and cannot tell you,
- 2) Skin cancer and genes,
- 3) Your rights if you take part in genetic research, and
- 4) Your decision to be tested or not.

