Overall data processing and missing data imputation. We will first examine aspects of data quality and distributional assumptions to ensure statistical integrity and accuracy: 1) data skewness, kurtosis, and parametric assumptions; 2) intention-to-treat (ITT) principles; 3) missing data considerations; and 4) control of potentially inflated Type-I errors due to multiple statistical tests. First, data skewness and kurtosis will be examined to determine whether each variable significantly deviates from normality. If so, we will employ data transformations by taking a log or square root of the skewed variables, or by using the Box-Cox transformation or kernel estimation techniques (Diggle et al., 2002) to determine the best-fitting parametric density. Second, we assume that up to 20% of the respondents will be unreachable at our three-month follow-up assessment; missing assessments may be amenable to imputation by several powerful techniques that can handle both continuous and categorical data (Graham et al., 2997; Schafer and Olsen, 1998). A related approach is the use of Hierarchical Linear Models (HLM) (Raudenbush and Bryk, 2002) to use all available behavioral outcomes data since HLM does not carry out list-wise deletion by default, thus the statistical power loss due to missing data may be minimal. We will apply the intention-to-treat (ITT) principle (Nich and Carroll, 1997). An ITT analysis in Aim I (Nich and Carroll, 1997; Willett et al., 1998) would assume missing data is related to lack of sun protection adherence. We may use the Pattern-Mixture Model to examine whether or not missed follow-up assessments are associated with baseline characteristics with safeguards to minimize

model overfit (Hedeker and Gibbons, 1997). Finally, to control for potentially inflated type-I error rate due to multiple comparisons, analyses can also incorporate a multiple comparisons method, such as a False Discovery Rate-controlling procedure, which is more powerful than simple Bonferroni corrections.

References for Data Processing

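### The plan does not say that the Aim I comparison of the randomised arms adjusts for the baseline outcome and the ethnicity balancing factor; doing so would improve precision at no cost

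*Combined protocol and SAP*

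**What the plan says.** - **Contrast.** Section 3, Aim I: "we hypothesize that behaviors and putative mediators will be higher in those who test, compared to those who decline testing or wait-list controls". This names testers, decliners and controls, not the two arms. The commitment to intention-to-treat in section 13 points to a comparison by arm but does not define it.
- **Allocation.** Section 8C: "randomized and balanced across Hispanic and Non-Hispanic ethnicity, n=120 in control arm, n=530 in PGT-SC arm".
- **Measurement.** The endpoint table in section 9 lists the sun protection items (five-point scales) and provider screening (yes/no) at both baseline and 3 months. Communication and threat/control beliefs are also listed at both times, but their 3-month entries are restricted, to interest in genetic information and to the risk perception question respectively.
- **Model.** The data-processing paragraph of section 13 is the only analysis text. It covers transformations, imputation, pattern-mixture models and false discovery rate control. On the model it says: "A related approach is the use of Hierarchical Linear Models (HLM) (Raudenbush and Bryk, 2002) to use all available behavioral outcomes data". It gives no outcome vector, time terms or covariates.
- **Attrition.** Section 13: "we assume that up to 20% of the respondents will be unreachable at our three-month follow-up assessment".
- **Predictors.** The only predictor list for a sun protection analysis belongs to Aim Ia, the subgroup with average-risk results.
- **Pilot.** Section 4: "Non-Hispanic Whites reported more consistent use of sunscreen", and more prior provider examinations, than Hispanics and other groups (all p < 0.01).

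**The concern.** The control arm is small: 120 randomised, and about 96 followed if 20% are lost. It sets the limit on the precision of any comparison by arm, so the baseline measurements already being taken are worth using. With the plan silent, an analyst could compare 3-month levels, or fit a hierarchical model to both visits and read off the arm-by-time term. With two visits and complete data, that term is the difference in mean change. Both are legitimate, but both are less precise than an analysis that conditions on the baseline value.

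The balancing factor matters for a second reason. If ethnicity predicts the outcome and allocation is balanced on it, a standard error that ignores it tends to be too large.

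Silence also leaves the choice of covariates open until after the data are seen, across several Aim I outcomes.

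**Working it through.** **The plan's own figure.** The plan states no power or precision figure for Aim I. Its one sample-size result is in section 8C: "Sample size estimates indicate that a total number of participants of 885 is necessary to evaluate our outcomes". It cannot be reproduced, because no alpha, power, effect size or SD is given. Nor does 20% loss link it to the 650 to be randomised: 885 × 0.8 = 708, and 650 / 0.8 = 812.5. It is not used below.

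**Inputs from the plan.** 530 and 120 randomised (section 8C); up to 20% loss (section 13), so 530 × 0.8 = 424 and 120 × 0.8 = 96.

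**Assumptions.** Complete cases; two-sided 5% and 80% power, so the multiplier is 1.960 + 0.842 = 2.80; equal SD at both visits; r from 0.3 to 0.7.

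**Level comparison.** SE = √(1/424 + 1/96) = 0.113 SD. Detectable difference = 2.80 × 0.113 = 0.317 SD. Power at 0.30 SD is 75.6%.

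**Variance factors relative to the level comparison.** Change: 2(1 − r). Baseline-adjusted: 1 − r². The adjusted detectable difference is 0.317 × √(1 − r²). The extra participants needed are 1/(1 − r²) − 1 for a level analysis and 2/(1 + r) − 1 for a change analysis.

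| r | Change factor | Adjusted factor | Variance saved vs level | Extra participants, level | Extra participants, change | Adjusted detectable difference | Adjusted power at 0.30 SD |
|---|---|---|---|---|---|---|---|
| 0.3 | 1.40 | 0.91 | 9% | 10% | 54% | 0.302 SD | 79.5% |
| 0.5 | 1.00 | 0.75 | 25% | 33% | 33% | 0.274 SD | 86.5% |
| 0.7 | 0.60 | 0.51 | 49% | 96% | 18% | 0.226 SD | 96.1% |

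The ordering does not depend on r. For any r between 0 and 1, 1 − r² is below 1, and (1 − r²) / [2(1 − r)] = (1 + r)/2 is also below 1.

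**Scale.** These savings are in variance. At r = 0.5 the confidence interval narrows by 1 − √0.75 = 13.4%.

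**Ethnicity alone.** For a 50:50 stratum, as in the section 6 recruitment table, and an assumed ethnic difference of d SD, the share of variance explained is 0.25d² / (1 + 0.25d²). That is 0.01/1.01 = 1.0% at d = 0.2 and 0.0625/1.0625 = 5.9% at d = 0.5.

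**If everyone randomised is analysed.** With 530 versus 120, SE = √(1/530 + 1/120) = 0.101 and the detectable difference is 0.283 SD unadjusted, or 0.283 × √0.75 = 0.245 SD at r = 0.5. The percentage saving at a given r is unchanged.

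**The case against.** The strongest reply is that the plan specifies no Aim I model at all, so it cannot be shown to lose anything. That stands against a reading that a reader might well reach: that the plan leaves the baseline value and the stratum out, and so throws away about a quarter of its precision. The documents do not support this. Neither covariate is included or excluded. The hierarchical model is offered to retain all available outcome data, which can include the baseline visit; with a common baseline mean across arms it would have roughly the adjusted variance. The quarter is r² at one assumed correlation, on the variance scale only.

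Other limits also stand:
- Aim I as worded is not the randomised contrast, so the comparison by arm must itself be written down.
- The formulas apply to scores. Provider screening is binary and needs its own analysis.
- Some belief and communication items appear not to be repeated at 3 months.
- The 424 versus 96 basis assumes complete cases. Section 13 also contemplates imputation, and an intention-to-treat analysis that links missingness to not protecting against the sun. Imputing on that basis would alter both the numbers analysed and r.
- The pilot compared Non-Hispanic Whites with everyone else, which is not the Hispanic/Non-Hispanic split, so it supports the prognostic value of the stratum only indirectly.

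The reply does not make the silence harmless. No common-baseline constraint is stated, and two natural readings of the text lead to a less precise analysis.

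**Conclusion.** The point holds as a gap in specification with a free improvement attached, not as an error in a chosen analysis. For score outcomes measured at both visits, adjusting for the baseline value is more precise than either a level or a change comparison at any correlation between 0 and 1. The size depends on a correlation that the plan does not state: against a level comparison, a variance reduction of 9% to 49% over r = 0.3 to 0.7, with 25% at the midpoint. The stratum contributes little, about 1% to 6% of variance for assumed ethnic differences of 0.2 to 0.5 SD; the main reason to include it is to keep the standard error correct under balanced allocation. No figure is claimed for provider screening or for items without a matching baseline value.

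**What to change.** Add to section 13, in substance: *For each Aim I outcome measured at both baseline and 3 months, the arms as randomised are compared in a regression on arm, the baseline value of the same outcome and the Hispanic/Non-Hispanic stratum used at randomisation. The regression is linear for scores; for provider screening it is logistic, reported as a standardised risk difference. For items without a matching baseline value, adjustment is for the stratum only.*

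If the hierarchical model is preferred, state instead that both arms share a common baseline mean and that the stratum is included.

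The cost is a few sentences. No new data, visits or participants are needed. The wording also fixes the contrast as 530 versus 120, which Aim I does not currently do; any comparison of testers with decliners would then need its own description.

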Primary endpoints are based on the 3-month follow up questionnaires. The primary study endpoints include personal utility of Personal Genomic Testing for Skin Cancer (PGT-SC) in terms of short-term (three months after testing) sun protection, skin screening (i.e., behaviors), communication, melanoma threat and control beliefs (i.e., putative mediators of behavior change), as well as differential reach of PGT-SC across Hispanics and non-Hispanics, as well as potential explanations for any differential reach. These will include the construct/measures listed below:

Construct/Measure	Prior work/psychometrics	Assess point
Sun protection and skin screening (Sunscreen, shade seeking, clothing and hat usage) on separate 5-point scales (never-always); health provider screening (no/yes).	Item reliability $\geq 80\%$. (Ganz, 2008)	B, 3-month
Family/physician communication. Frequency, content of communication with physicians, family, and friends regarding skin cancer risk, interest in genetic information; 4-point scales (not at all-a lot).	Items used with high comprehensibility in population-based studies ([name] 2005, 2009, 2012, 2014)	B, 3-month, (interest in genetic information only)

Perceived skin cancer threat belief (Witte 1996). Includes assessment of risk perceptions (verbal, percent likelihood, comparison) on separate scales (5 to 10-point) from low-high, with “don’t know” option (Waters 2013); worry, assessed with 4-point items (never-all the time). Perceived skin cancer control beliefs (Witte 1996) Includes skin cancer prevention self-efficacy (7 items, on separate 4-point scales; not at all-extremely capable), skin cancer prevention response-efficacy (7 items, on separate 4-point scales; not at all to extremely important).
	
Widely used perceived risk items drawn from prior health behavior research (Weinstein 1982), Lerman’s cancer worry scale (Lerman 1991), and perceived cancer severity (Aiken 1994). Control belief items (Bandura 1986) predicting uptake of cancer prevention behaviors; adapted for skin cancer prevention ([name] 2006).
	
B, 3-month (risk perception question only)

Hispanic ethnicity
	
For initial sampling frame (50%) Hispanic, self-report as per Baseline survey.
	
B

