Cognitive interviews to ensure high comprehensibility and acceptability of the translations will be conducted by [name] and [name].

The Department of Psychiatry & Behavioral Sciences at MSKCC will conduct data analysis on de-identified data.

11) Study Methods

*The timeline above gives very detailed information about study methods.

Subjects will be approached at their Clinic and asked if they are interested in participating. Individuals accompanying Clinic patients and who attend another UNM Clinic are eligible to participate.

They will then discuss the study with the bilingual interviewer and, if they are eligible agree and sign informed consent. All baseline surveys will then be completed with the PA in the clinic.

Identifiers will be collected and remain at UNM for mailing and follow-up. Subjects will then be de-identified at the end of the study (after 3 years).

Subjects will receive compensation for participation. ALL consented subjects will receive a \$15 Target Gift card after completion of the Baseline Questionnaire; those in the randomized to the wait list control Group 1 will receive compensation for the baseline survey and the three-month survey. Those randomized to Group 2, the PGT-SC arm will then be given information modules through the internet (or on paper if they prefer). They will be asked if they would like to participate in genetic testing for MC1R. Those randomized to receive PGT-SC who complete the online educational modules will be compensated \$5 Target Gift card per educational module, with a maximum of \$15 possible.

Additionally, among those who elect genetic testing, we will assess distress levels two weeks after the PGT -SC genetic results have been received, and will compensate participants for their time with a \$5 target Gift card. All participants who completed Baseline Assessments (whether tested or not) will be contacted for the final assessment by telephone approximately three months after recruitment.

Participants who complete the three-month outcome assessment will receive a \$15 Target Gift card. This level of compensation is reasonable for the level of effort required for subjects.

12) Data and Specimen Banking

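### Section 13's intention-to-treat wording for Aim I appears to count missing three-month data as no sun protection and names no primary missing-data method, so loss that differs by arm could create a false difference

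*Combined protocol and SAP*

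**What the plan says.** **Missing data (Section 13, data processing and imputation).** The plan expects loss: "we assume that up to 20% of the respondents will be unreachable at our three-month follow-up assessment". It gives no split by arm. It then states firmly "We will apply the intention-to-treat (ITT) principle", and adds that for Aim I such an analysis "would assume missing data is related to lack of sun protection adherence". Three other approaches appear in the same paragraph, all as possibilities:
- imputation;
- hierarchical linear models (HLM) on all available data;
- a pattern-mixture model, to see whether missed assessments relate to baseline characteristics.

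None is named as primary. No value is given for a missing person, and no sensitivity analysis is set for loss that differs by arm.

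**Outcome (Section 9).** Three-month sun protection is among the primary endpoints. Its items are recorded "on separate 5-point scales (never-always); health provider screening (no/yes"). No dichotomy is defined.

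**Arms and contacts.** Section 8 C randomises "n=120 in control arm, n=530 in PGT-SC arm". Follow-up is by telephone. The PGT-SC arm can earn up to $15 for the educational modules and, if tested, $5 for a two-week call. In Section 11, "those in the randomized to the wait list control Group 1 will receive compensation for the baseline survey and the three-month survey". Both arms receive the same $15 for the three-month assessment. Section 8 F offers controls the test directly after that assessment.

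**The concern.** ITT settles who is analysed and in which arm. It does not supply a value for an outcome nobody observed. Here a missing outcome means an unanswered telephone call, which says little about sunscreen, hats or shade.

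If unreachable people are scored as not protecting, each arm's result becomes its true rate multiplied by its retention. A difference in retention then looks like a difference in behaviour, on a primary endpoint. The arms differ in contacts and incentives, so unequal loss is plausible.

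The listed alternatives do not settle the matter. Imputation and HLM normally rest on missing at random, which is a different assumption from the one in the ITT sentence. With no method named as primary, the choice could be made after results are seen.

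**Working it through.** **Plan's own figure.** The only sample-size result is in Section 8 C: "Sample size estimates indicate that a total number of participants of 885 is necessary to evaluate our outcomes". No alpha, power, effect or standard deviation comes with it, so it cannot be rebuilt. The randomised total is 120 + 530 = 650. Allowing for 20% loss gives 650/0.80 = 813, and 885 × 0.80 = 708; neither links 650 to 885. That conflict is a separate matter. The calculations below use 650.

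**Inputs from the documents.** Arm sizes are 530 and 120 (Section 8 C), and loss is up to 20% (Section 13). Section 4 gives the pilot rates: "29% reported that they consistently used sunscreen, 62% wore a shirt with sleeves, 34% a hat, and 47% sought shade often or always".

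**Assumptions.** Two-sided alpha is 0.05. Missing is scored as not protecting on a yes/no outcome. The loss splits and the 15-point effect are also assumed. Loss is unrelated to outcome unless stated otherwise.

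**Step 1: no true effect, unequal loss.** Write p for the true rate and m for loss, with subscripts T for PGT-SC and C for control.
- Rate under the rule = p(1 − m).
- False difference = p(m_C − m_T).
- Standard error (SE) = √[r_T(1 − r_T)/530 + r_C(1 − r_C)/120], where r is the rate under the rule.
- Type I error = Φ(z − 1.96) + Φ(−z − 1.96), with z = difference/SE.

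Overall loss:
- 19%/24%: (530 × 0.19 + 120 × 0.24)/650 = 19.9%.
- 18%/28%: (530 × 0.18 + 120 × 0.28)/650 = 19.8%.

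Worked case, p = 0.47 with 18%/28% loss: r_T = 0.47 × 0.82 = 38.5% and r_C = 0.47 × 0.72 = 33.8%. The difference is 4.7 points, SE 4.8 points, z = 0.98, and type I error about 16%.

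| Pilot rate | 19% vs 24% loss: false difference, type I error | 18% vs 28% loss: false difference, type I error |
|---|---|---|
| 29% (sunscreen) | 1.5 points, 6% | 2.9 points, 11% |
| 34% (hat) | 1.7 points, 7% | 3.4 points, 12% |
| 47% (shade) | 2.4 points, 8% | 4.7 points, 16% |
| 62% (sleeves) | 3.1 points, 9% | 6.2 points, 23% |

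A pooled-variance test changes these error rates by about one percentage point at most. If loss is higher in the PGT-SC arm, the sign reverses.

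**Step 2: how far this depends on who is missing.** Let q be the true rate among the missing, equal in both arms. The bias of the rule is q(m_C − m_T). With an observed rate of 47% in both arms and 18%/28% loss:
- q = 47%: bias 0.47 × 10 = 4.7 points.
- q = 23.5% (half the observed rate): bias 0.235 × 10 = 2.35, about 2.4 points.
- q = 0: no bias.

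In the half-rate case the true arm rates are 0.385 + 0.18 × 0.235 = 42.8% and 0.338 + 0.28 × 0.235 = 40.4%, so the true difference is 2.35 points. An observed-data analysis without covariates would show 0. It would be off by the same amount in the other direction.

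**Step 3: true effect, equal 20% loss.**
- 0.62 × 0.80 = 49.6% and 0.47 × 0.80 = 37.6%, so 15 points become 12.
- Power under the rule (530 vs 120): SE 4.93, z = 2.44, power about 68%.
- Power on observed cases (530 × 0.80 = 424 vs 120 × 0.80 = 96): SE 5.61, z = 2.67, power about 76%.
- Odds ratio: 1.84 becomes 1.63.
- Risk ratio: 0.62/0.47 = 0.496/0.376 = 1.32, unchanged.

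**The case against.** **The text does not state a scoring rule.** It says that missingness is related to non-adherence, not that it is scored as such. The next sentence mentions a pattern-mixture model, which fits an informative-missingness reading. This stands. A reader might infer that the plan fixes missing as non-adherent, or as the lowest score. The documents do not go that far. If only informative missingness was meant, the size of any bias is undefined, but the plan then gives no way to analyse it.

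**The direction of unequal loss is not established.** The extra paid contacts could help retention in the PGT-SC arm. Equally, controls get the test offer only after the three-month assessment, which could raise theirs, and both arms are paid the same for it. This stands. A reader might infer that the rule favours PGT-SC, and the documents do not support that.

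**The rule may be right.** If the unreachable truly do not protect themselves, it gives the correct answer and a missing-at-random analysis is the biased one. This stands as a possibility. It is a reason to show both analyses, not to build one into the definition of ITT.

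**Better methods are already listed.** They are, so much of the remedy is choosing among them. But they are optional and none is designated as primary.

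**The contrast is not clearly 530 vs 120.** The Aim I hypothesis in Section 3 sets those who test against decliners or wait-list controls. The ITT commitment supports the as-randomised comparison used here, but the figures would differ for the other contrast.

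**Conclusion.** The concern holds in conditional form. The one firm missing-data statement for Aim I attaches to ITT an assumption that ITT does not need, its meaning is unclear, and no method is primary. If missing is scored as not protecting and some missing people do protect themselves, loss gaps of 5 to 10 percentage points give false differences of 1.5 to 6.2 points and type I error of 6% to 23% across the four pilot rates. Equal 20% loss turns a true 15-point difference into 12 and costs about 8 points of power.

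All loss splits, the alpha and the effect size are assumptions. The yes/no outcome is a simplification of the 5-point items, and figures on that scale would depend on an assumed code for missing, so none are relied on here. It would also be too strong to say that every true effect shrinks by the retention rate. That applies to the risk difference when loss is equal by arm and unrelated to outcome; the risk ratio does not change.

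**What to change.** Replace the sentence in Section 13 that links ITT to non-adherence, and state the following:
- **Primary Aim I analysis:** all 650 participants compared as randomised, under missing at random. Use either multiple imputation by arm or a baseline-adjusted likelihood model; choose one in advance. Include baseline behaviour, ethnicity, language, literacy and demographics, all already collected (Section 9).
- **Sensitivity analysis 1:** missing counted as not protecting, labelled as such, with the value to be assigned on the 5-point items written down.
- **Sensitivity analysis 2:** a delta-adjusted analysis that varies the assumed outcome among the missing separately by arm.

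The cost is plan wording and modest extra analysis, with no new data or participants. The downside is that the primary result rests on missing at random. Step 2 of the working shows that this can also be wrong, and the two sensitivity analyses are there to probe it.
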